4.1. Rationale for Trial Design

The double-blind randomized controlled trial (RCT) is accepted by the authorities as objective scientific methodology that, when ideally performed, produces knowledge untainted by bias. The most important design techniques for avoiding bias in clinical trials are blinding and randomization, and these should be normal features of most controlled clinical trials intended to be included in a marketing application. Most such trials follow a double-blind approach, in which treatments are pre-packed in accordance with a suitable randomization schedule and supplied to the trial center(s) labelled only with the subject number and the treatment period so that no one involved in the conduct of the trial is aware of the specific treatment allocated to any particular subject, not even as a code letter. The baseline characteristics will be summarized using descriptive statistics to facilitate evaluation of possible differences between treatment groups, which might bias the comparison of treatments. Study medication compliance, protocol violations and reasons for dropouts will be examined both as indicators of treatment differences and to evaluate any biases in the proposed treatment comparisons.

4.2. Trial Population

4.2.1. Selection of Trial Population

Adults, both sexes, aged 18-65 years of age.

4.2.2. Rationale for Trial Population

Cholera predominantly affects children and young adults²⁰. The paediatric population is outside of the scope of the current protocol, however, during the outbreak all age groups are at risk of infection. With this consideration, capping the age at 65 years will facilitate the recruitment, while allowing to reduce the burden and complications of co-managing chronic diseases associated with elderly populations.

4.2.3. Inclusion Criteria

- Signed informed consent.
- Adults, both genders aged 18-65 years.
- Acute watery diarrhea (defined as passage of three or more liquid stools within the 24 hours before admission) with severe dehydration on arrival.
- Detection of *V. cholerae* by rapid diagnostic assay (e.g. dark field microscopy).

4.2.4. Exclusion Criteria

- Known or suspected hypersensitivity to trial product(s) or related products.
- Subjects with passage of bloody stools or muco-purulent stools.
- Subjects with chronic diarrhea (>4 weeks of Diarrhea).
- Clinically significant concomitant systemic disease (i.e. cardiovascular diseases including heart failure, acute kidney injury, sepsis or life-threatening malignant cancer).
- Mental incapacity, unwillingness, or language barriers, precluding adequate understanding or cooperation.
- History of receiving antimicrobial or antidiarrheal drugs within 6 hours prior to admission.
- Positive urine pregnancy test for all female patients
- Failure to obtain informed consent.
- Failure to definitively diagnose cholera via culture or RT-PCR

4.2.5. Screen Failures

Patients with acute diarrhea, who go through the screening but do not fit the inclusion criteria or present with criteria excluding them from the clinical trial as per sections 4.2.3 and 4.2.4 above would be labelled as screen failures and will not receive the study treatment and will receive standard treatment in the hospital. Screen failures are not expected to contribute to the analysis of efficacy and safety. Screen failures who have medical conditions will be referred to the appropriate level of care.

4.3. Sequence of events

- All prospective patients visiting the facilities aged 18-65 years experiencing acute watery diarrhea (duration 24 hours or less) and severe dehydration will be assessed. Assessment will be done primarily by the study nurses (at least three nurses will rotate for the study duration). Study doctors will also assist with the assessment.
- Consent will be sought from suspected patients to enroll cases. Confirmatory microbiology for cholera will be done. Eligibility of the participants will be identified using the screening tool. This study will not include vulnerable participants (refer to inclusion and exclusion criteria in sections 4.2.3 and 4.2.4).
- Trained nurses/study doctors will take the patients (who fulfil all inclusion criteria and do not meet any of the exclusion criteria) or guardian for critically ill patients through the consenting process. This will involve explaining in plain language what the study is about and the risk/benefits of participating. Participants will be informed that participation in the trial is voluntary and that they can withdraw at any time during the 3 days of inpatient care. They will be required to sign applicable consent forms, one form will be kept by investigators and another will be given to participants.
- Upon consenting, randomization will be done by the independent researcher and treatment started by the study nurses in consultation and supervision by study doctors, in addition to standard management for *V. Cholerae* for patients.
- All patients will be admitted in the dedicated wards of the study site for all the 3 days of treatment. Early discharges will not be permitted for enrolled study participants due to safety and endpoint measurement reasons. To facilitate data analysis, and in particular safety analysis (development of possible adverse events, while undergoing treatment with VR-AD-1005), all

participants with different level of severity of the disease must follow the same treatment protocol. Having variations in the treatment strategy, such as early discharge, may complicate the conduct of the trial. An example of such complication is the development of unrelated AEs which stem from changes in the lifestyle of participants after discharge, for example, change in diet or a community-acquired disease, which will be prevented and avoided by having all participants as in-patients.

- Patients will receive their first dose administered by the study nurse immediately after the consenting process and randomization is completed. The treatment is in a capsule form and participants will be instructed by the study nurse to swallow the treatment whole without chewing with a glass of water or oral rehydration solution. The volume of liquid used for ingesting the treatment will be recorded in patient water intake charts for monitoring and analysis purposes. Subsequent doses will be timed based on the first dose (i.e. second dose is 3 hours after first dose). The study nurses will record the timing for each patient's medication and will keep strictly to the timing between shifts by handing over study patient folder records after each shift. Study nurses will additionally monitor for vomiting or accidental loss of treatment dose (for example, dropped dose) and to re-administer, if vomiting occurs within 30 minutes of treatment administration or if the pill is clearly visible in the vomit.
- Stool samples will be taken to the laboratory for culture and identification of *V. cholerae* and blood samples taken for study laboratory assessments. Laboratory assessments will be conducted at the icddr, Immunobiology, Nutrition and Toxicology Laboratory and/or diagnostics laboratories. Any other necessary study laboratory test may be performed at any of these laboratories depending on capacity and efficiency of study procedures.
- During the three days of admission, participants will be monitored daily by study doctors and nurses. Treatment will be given as per scheduled doses each day, monitoring and measurement of water intake, weighing of vomiting and stool output using calibrated scales (scales will be calibrated on daily basis) and all other study procedures. For recruited patients whose culture comes back negative for cholera, treatment will be stopped (culture results expected by day three) and they will not be included in the final analysis.
- In the event of SAE's during treatment or after discharge, participants will be referred to the appropriate clinic for comprehensive management.
- Participants will only be discharged when the study doctors deem so after the three days of treatment. Participants who are not discharged after 3 days will not receive further treatment but will be monitored by study staff.
- After discharge, participants will be followed up with weekly phone calls to check on their health and wellbeing and also ascertain, if they are experiencing any side effects of the treatment. For participants without phone, the phone number of their guardian or neighbor will be taken for the follow up. Where participant cannot be reached via phone, their personal address will be followed to conduct the follow up. After three attempts of phone calls and one home visit, participants that cannot be reached will be declared lost to follow up.

[REDACTED]

[REDACTED]

[REDACTED]

[REDACTED]

[REDACTED]

[REDACTED]

[REDACTED]

[REDACTED]

[REDACTED]

[REDACTED]

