4.4.4. Dosing and Administration

Cholera typically presents with voluminous liquid stool due to hypersecretion of fluids by the intestine²¹. VR-AD-1005 is not absorbed and acts at the level of intestinal mucosa. Thus, first dose of the drug is dissolved in much larger than normal volume of fluid presented in the intestine of a patient recently admitted for cholera. In addition, due to the diarrhea, first dose of the drug is evacuated with stool faster than subsequent doses. In order to maintain working concentration and counteract dilution, first dose of the drug is tripled, representing the "loading dose" drug administration tactics. The remaining doses are single doses for the three days which is in line with average duration of the cholera episode and thus gives sufficient time for the drug to exert its effect. The treatment will be administered to participants under the supervision of trained study personnel, i.e. study nurse. Nurses will be instructed to monitor for vomiting or accidental loss of treatment dose (for example, dropped dose). The participants will be instructed to swallow the treatment whole without chewing with a glass of water or oral rehydration solution. The volume of the liquid will be registered in the water intake charts.

Administration begins when the patient is able to swallow the tablet. If the patient vomits less than 30 minutes after administration of dose, the dose will have to be re-administered after about 15 minutes. If the patient vomits after 40 minutes, the clinician will check the vomitus to see if the medication is in there, if the medication is not visible then the dose is not re-administered. If the medication is visible, then the dose is re-administered after 15 minutes. Both arms will receive extra doses of the medication for these purposes. In the event of lost dose, the pharmacy will have a backup of the medication doses for emergency purposes.

VR-AD-1005 oral dose will be administered orally 4 times per day (approximately every 4-5 hours with overnight break to allow for participants rest and recovery) with first administration of 3 capsules as loading dose. Dosing is indicated in the table below (**Table 3**), with reasonable timing of administration at 7:00, 12:00, 17:00 and 21:00 hours \pm 1 hour.

Table 3: VR-AD-1005 doses and dosing schedule

Time	Day 1	Day 2	Day 3
Time 0 hr	3 doses	1 dose	1 dose
Time +5:00 hr	1 dose	1 dose	1 dose

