4.5. Trial Assessments and Procedures

4.5.1. Screening/Baseline Assessments and Procedures

- Medical history: All patients admitted with secretory diarrhea with severe dehydration will be offered to participate in the study.
- Informed consent. Severely ill patients unable to sign the consent form will be resuscitated according to the proper SOPs, until they are able to make an informed decision regarding the enrollment.
- Randomization and assignment to treatment Group. IP assignment.
- Concomitant medication review.
- Physical examination: height, body weight, temperature, thirst, HEENT (note and record signs of dehydration, such as sunken eyes), skin (note and record signs of dehydration, such loss of turgor), level of consciousness using AVPU (active, response on voice or pain, unconscious) criteria, vomiting.
- Hydration status should be assessed in each participant including assessment of IV fluids, oral ORS intake and oral water intake.
- Vital signs: body temperature, heart rate, respiratory rate, blood pressure (including orthostatic blood pressure measurement when possible), urine output.
- Blood collection (5 ml) for Complete Blood Count (CBC), Basic Metabolic Panel (BMP) including serum electrolytes and creatinine.
- Stool collection for *V. cholerae* RDT (dark field microscopy) and culture.
- Initiate Re-hydration and antibiotic treatment in accordance with the SOPs for cholera patients until recovery.
- Initiate IP administration as soon as participants can tolerate oral intake.

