of IP/placebo, physical examination will be performed and vital signs will be obtained for initial three hours followed by at least 8 hourly for the whole treatment period and also at the end of treatment. Assessment of hydration status, including dehydration, vomiting, urine output, water intake, ORS intake or IV fluid infusion will be performed throughout the treatment period. Concomitant medication review will also be performed at least once in a day. Blood testing for the re-evaluation of the patient will be done according to the clinical condition of the patient and once at the end of treatment. Beside giving study specific treatment, all patients will be provided standard care and treatments. Standard of care (SoC) for adult cholera patients having severe dehydration includes rehydration with IV cholera saline (100ml/kg over 3 hours) and Doxycycline 300 mg after initial hydration; SoC also includes replacement of ongoing purging with ORS (if no persistent vomiting or no high purging) or IV fluid (if there is persistent vomiting or high purging). Adverse events, including SAE will be closely monitored, and appropriate treatment will be provided; if needed, patients will be referred to specialized clinics or hospitals. Recovery from diarrhoea will be assessed continuously through stool output and frequency, and stool culture will be performed to confirm the absence of *V. cholerae*. Feeding with a normal diet will be continued /initiated based on clinical feasibility; feeding with a normal diet will be resumed when vomiting has stopped and patients are able to tolerate oral intake. Patients will be fed meals prepared and dispensed under hygienic conditions. Street food will be prohibited due to the high risk of bacterial contamination, which may hinder case management and also invalidate the results of this study. Patients will receive 2 to 3 cooked meals per day. Even after discharge, health and wellbeing of the participants will be followed up with weekly phone calls or home visits; it will be ascertained if they are experiencing any side effects of the treatment or any other AE or SAE.

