4.10.3. Antibiotic Therapy

Stool samples for *V. cholerae* dark field microscopy and culture should be collected before the onset of antibiotic therapy for presumed cases of cholera (Profuse watery stools, typically looking like 'rice water', resulting dehydration; many individuals affected in the same locality).

- Adults : Azithromycin, 1 gram single dose orally
- Repeat dose if vomiting within 1/2 hour of taking the medicine

Do not use azithromycin when a patient is 60-65 years or older or at any age with an established heart disease to avoid adverse effects, specially conduction defects.

In such a case, Doxycycline 300 mg single dose is recommended.

Antibiotics should be administered no sooner than 2 hours after taking VR-AD-1005.

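### Dose timing and the background antibiotic are each stated in two incompatible ways, so treatment, adherence and deviations have no single reference regimen

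*Combined protocol and SAP*

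**What the plan says.** **Dose timing.** Section 4.3 fixes the start by the patient: "Patients will receive their first dose administered by the study nurse immediately after the consenting process and randomization is completed". It then says "Subsequent doses will be timed based on the first dose (i.e. second dose is 3 hours after first dose" and adds that nurses "will keep strictly to the timing between shifts". Section 4.5.1 also leaves the start to the patient's condition: "Initiate IP administration as soon as participants can tolerate oral intake". Section 4.4.4 prescribes four administrations a day, about 4 to 5 hours apart with a night-time pause, and offers "reasonable timing of administration at 7:00, 12:00, 17:00 and 21:00 hours", each within 1 hour. Table 3 in the same section, and the column heads of Appendix I, place the doses at 0, +5, +10 and +15 hours on each of three days.

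**Antibiotic.** Section 4.9 describes standard of care for adult cholera with severe dehydration as intravenous rehydration and "Doxycycline 300 mg after initial hydration", with no condition of age or cardiac history. Section 4.10.3 reads "Adults : Azithromycin, 1 gram single dose orally" and reserves doxycycline 300 mg for patients aged 60-65 or older, or with established heart disease at any age. The management table in section 4.10.2 makes an antibiotic conditional on need. Section 4.10.3 also sets a spacing rule: "Antibiotics should be administered no sooner than 2 hours after taking VR-AD-1005".

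No visible text says which section takes precedence.

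**The concern.** These are operative bedside instructions for severely dehydrated patients, and section 4.3 itself requires all participants to follow the same treatment protocol. The primary outcome is stool output from the first dose onward, analysed in total and by 12-hour period (sections 5.0 and 6.2.1). Spacing after the tripled first dose and the choice of antibiotic both fall inside that window. Staff working from different sections could treat similar patients differently and each be compliant with the page in front of them.

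The plan also relies on a notion of adherence. Significant non-compliance is a ground for withdrawal (section 4.11), deviations touching safety or endpoints must be reported promptly (section 4.13), and the analyses are repeated in a per-protocol population (sections 6.2.1 and 6.3). Each of these needs one regimen to judge against.

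**Working it through.** The plan gives no figure to reproduce here. The check sets the instructions side by side and does simple arithmetic on the times. Sample size, power and alpha play no part.

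**Inputs.** Second dose at +3 h (section 4.3); interval 4-5 h and clock times 07:00, 12:00, 17:00, 21:00, each ±1 h (section 4.4.4); offsets 0, +5, +10, +15 h (Table 3, Appendix I). Section 4.3 gives no times for doses three and four, so its 3 hours is applied to the first gap only. Table 3 offsets are taken as exact.

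**Step 1: nominal gaps.**
- Clock times: 12−7 = 5, 17−12 = 5, 21−17 = 4 h; overnight 24−21+7 = 10 h.
- Table 3: 5, 5, 5 h; overnight 24−15 = 9 h.
- The fourth dose is at 21−7 = +14 h by clock and +15 h by table, a difference the 1-hour window absorbs. The 4-5 h text, the table and the clock times therefore agree for a 07:00 start.
- The 3 h gap lies outside 4-5 h. In the 07:00 and 12:00 slots it arises only at the edge of the windows (08:00 then 11:00, or 13:00 then 16:00). Between the 17:00 and 21:00 slots it fits.

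**Step 2: anchor.** Let the first dose be at time *t*. For the four Table 3 doses to meet the clock windows:
- *t* in 06:00-08:00
- *t*+5 in 11:00-13:00, so *t* in 06:00-08:00
- *t*+10 in 16:00-18:00, so *t* in 06:00-08:00
- *t*+15 in 20:00-22:00, so *t* in 05:00-07:00

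Together these require *t* between 06:00 and 07:00. Starting in a later slot fails because a dose falls in the night: 12:00+15 = 03:00, 17:00+10 = 03:00, 21:00+5 = 02:00, none within any window.

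| First dose | Second dose by 4.3 | Doses 2-4 by Table 3 | Next clock slots |
|---|---|---|---|
| 07:00 | 10:00 | 12:00, 17:00, 22:00 | 12:00, 17:00, 21:00 |
| 12:00 | 15:00 | 17:00, 22:00, 03:00 | 17:00, 21:00, 07:00 |
| 19:00 | 22:00 | 24:00, 05:00, 10:00 | 21:00, 07:00, 12:00 |

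For the 07:00 and 12:00 starts, the 3-hour dose (10:00, 15:00) lies outside the next clock window (11:00-13:00, 16:00-18:00). For the 19:00 start, 22:00 is inside 20:00-22:00 but 24:00 is not, and Table 3 loses the overnight pause. Before 07:00 the next morning, that is in the first 12 hours, Table 3 gives 3+1+1 = 5 doses and the clock gives 3+1 = 4, if the patient takes the 21:00 slot.

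**Step 3: antibiotic, by patient type.**
- Adult under 60, no heart disease: section 4.9 leads to doxycycline, section 4.10.3 to azithromycin.
- Exception group: both lead to doxycycline 300 mg.
- Any severely dehydrated adult: section 4.10.2 makes the antibiotic conditional, while the other two name one.

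Inclusion is 18-65 years with severe dehydration, and clinically significant cardiovascular disease is excluded (sections 4.2.3, 4.2.4). The conflict therefore covers most of the eligible age range.

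**Step 4: interaction.** After the 2-hour wait in section 4.10.3, a 3 h interval leaves 3−2 = 1 h before the second study dose and a 5 h interval leaves 5−2 = 3 h. The unresolved dose interval also affects where the antibiotic can go.

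**The case against.** The best defence is that the discrepancy is narrow. The number of administrations per day and the tripled first dose are not in dispute. The 4-5 h text, Table 3, Appendix I and the clock times share a nominal interval, and the clock times are offered as reasonable rather than mandatory. Part of section 4.4 is redacted, and the attached standard of care and hospital guidelines, which are not visible, may settle the antibiotic. Nurses already record dose times, and concomitant medication is reviewed at least daily. All of this stands as a limit on size. It does not remove the conflict: section 4.3 asks for strict timing, agreement among several statements does not show which one is right, and the anchor problem remains even if the 3 hours is set aside.

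A reader might infer more than the documents support:
- **Vomiting rules in conflict.** Sections 4.3 and 4.4.4 lead to the same action below 30 minutes and after 40; section 4.4.4 is merely silent in between, and section 4.3 covers that gap.
- **Antibiotic start in conflict with the 2-hour rule.** The Appendix I row covers rehydration and/or antibiotics and is ticked at every dosing time; section 4.5.1 gives no hour; sections 4.9 and 4.10.2 put the antibiotic after fluids. All can be met together with the spacing rule.
- **Per-protocol set undeterminable.** No visible text defines that set by dose interval or antibiotic, so this does not follow.
- **Biased comparison.** Both ambiguities apply equally to both blinded arms.

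**Conclusion.** Two contradictions in current operative text stand. For dose timing, the second dose is at 3 h or 5 h, and later doses follow either the first dose or the clock; with exact offsets the two anchors fit a full four-dose day only for a first dose between 06:00 and 07:00. For the antibiotic, adults under 60 without heart disease are assigned different drugs by sections 4.9 and 4.10.3.

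The expected consequence is extra variation in early exposure, and possibly in stool output, in both arms, plus adherence and deviation judgements without a common standard. The documents give no basis for putting a number on the effect on stool output or safety, and the conflicts alone do not produce directional bias. The conclusion assumes that neither the redacted text nor the attached standard of care sets a precedence. If one does, the protocol sections still need to be brought into line with it. The text is wrong as written and should be corrected, because it governs what severely ill patients receive during the primary-outcome window.

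**What to change.** 1. The clinical team reconciles section 4.3 with section 4.4.4, Table 3 and Appendix I to one dose-timing rule and one anchor, including what happens when the first dose is given in the afternoon or at night. This review takes no view on which rule is right.
2. The clinical team reconciles section 4.9 with sections 4.10.2 and 4.10.3 to one antibiotic instruction, including whether it is conditional and where the age limit of any exception lies. This review takes no view on which drug applies.
3. Record in the CRF the antibiotic given and its clock time relative to study drug. Assess adherence and deviations against the reconciled text.
4. Minor clarifications: state in section 4.4.4 the action for vomiting between 30 and 40 minutes, and cross-refer the 2-hour antibiotic spacing rule in section 4.5.1 and Appendix I.

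The cost is a protocol text correction with whatever ethics review it requires, a short instruction to nurses, and one or two CRF fields. Sample size, endpoints and analysis methods are unaffected.

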4.4.6 Participant Assignment, Randomization and Blinding

4.4.6.1. Participant Assignment

During recruitment, in addition to rehydration/antibiotics, each eligible participant will receive a numbered individual package of treatment, with package number being unique to the particular participant. After the end of the study for the purpose of data analysis the randomization tables will be supplied to the biostatisticians and data from all participants who have completed the trials will be assigned to the Group A (VR-AD-1005 intervention) or Group B (placebo) for analysis.

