If any serious adverse events occur before treatment phase, study treatment may be postponed at the researcher's decision.

The reason for participant discontinuation or withdrawal from the study will be recorded on the CRF. Subjects who sign the informed consent form and are randomized but do not receive the study intervention may be replaced. Subjects who sign the informed consent form, and are randomized and receive the study intervention, and subsequently withdraw, or are withdrawn or discontinued from the study, will not be replaced.

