5.0 Sample Size Calculation and Outcome (Primary and Secondary) Variable(s)

Clearly mention your assumptions. List the power and precision desired. Describe the optimal conditions to attain the sample size. Justify the sample size that is deemed sufficient to achieve the specific aims.

Planned screening is 500 participants. ITT (intention to treat) group is 150 patients. Enrollment will stop once 150 participants are recruited, or once 100% of per-protocol dataset (PP) is achieved. Sample size was calculated based on the mean volume of stool output in cholera patients. Mean stool output was assumed at 280 ± 156 g/kg²²⁻²⁴. Assuming 33% reduction (alternative hypothesis) vs no reduction (null hypothesis), sample size was calculated using GraphPad Prism software for two-tailed t-test with alpha 5% and power 0.8. Using recruitment of 50 participants per arm (100 total), power level of 0.82 can be achieved. Although, this is a sufficient level of power for the projected study, data points lost due to participant drop-out, cross-over to other study arms, withdrawal and missing data will affect the power of the study. We calculated that recruitment of up to 75 patients per study arm would allow power of 0.94.

Endpoints associated with primary and secondary objectives, and justification for endpoints are given below (Table 1).

Table 1-Primary and Secondary Objectives and Endpoints

OBJECTIVES	ENDPOINTS	JUSTIFICATION FOR ENDPOINTS
Primary		

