6.2. Analysis Supporting Primary Objectives

6.2.1. Statistical Model, Hypothesis, and Method of Analysis

Primary Endpoint:

Reduction in stool output volume over a treatment period.

Primary Endpoint 1., Hypothesis 1. Treatment with VR-AD-1005 reduces stool output in patients with diarrhea due to *V. cholerae* infection. Null hypothesis is stated as no statistically significant difference in stool output volume as compared to placebo; alternative Hypothesis 1 is stated as statistically significant reduction in stool output volume in patients treated with VR-AD- 1005.

Two analytical approaches are proposed. Approach 1 will be based on the total quantity of stool purged by participant during the intervention administration period. Stool output will be expressed as g/kg body weight based on the stool charts, and the means will be compared between intervention and placebo groups using Student's unpaired t-test. In approach 2, stool purging is measured and plotted as total stool output in ml/kg/12 hours based on the individual stool collection charts. Weight of stool will be converted to volume using 1:1 weight/volume ratio. Diarrhea of cholera resolves rapidly, and majority of patients are expected to recover within 30-50 hours after randomization. 12-hour analysis increments allow a better insight into the onset and timing of the effect of study intervention as compared to cumulative data over the duration of the treatment. Means will be compared for each 12-hour period after first intervention administration using unpaired Student's t-test. Normal distribution is assumed for both cases. Analysis will be conducted in the ITT, MITT and PP groups. Missing data and outliers will be handled using imputation technique. Non-adherence and lost to follow-up patients will be categorized into the appropriate group and handled accordingly. No subtractions will be made from the ITT group after randomization assignment.

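### Treated patients with a negative culture are dropped from the final analysis while ITT allows no subtractions, and no analysis set is defined or named as primary to settle which rule governs the result

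*Combined protocol and SAP*

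**What the plan says.** Section 4.2.3 admits patients on a rapid assay such as dark field microscopy. Under section 4.3 the first dose follows directly on consent and randomisation. Culture is read later, and for those "whose culture comes back negative for cholera, treatment will be stopped (culture results expected by day three) and they will not be included". The analysis meant is the final one, and the rule is not limited to any one analysis set.

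Section 4.2.4 lists as an exclusion criterion "Failure to definitively diagnose cholera via culture or RT-PCR". Section 4.2.5 calls anyone who meets an exclusion criterion a screen failure who gets no study treatment.

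Section 4.4.6.1 says that, once the randomisation tables are released, "data from all participants who have completed the trials will be assigned to the Group A" or to Group B. Section 4.6 defines completing the study as finishing all its phases.

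Section 6.2.1 plans analyses in ITT, MITT and PP and states: "No subtractions will be made from the ITT group after randomization assignment". Section 6.3 repeats the rule for the secondary endpoints. MITT and PP are defined nowhere, and no set is named as primary.

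Section 5.0 puts ITT at 150 and adds: "Enrollment will stop once 150 participants are recruited, or once 100% of per-protocol dataset (PP) is achieved". No number is given for the PP target. Section 4.11 says: "Subjects who sign the informed consent form and are randomized but do not receive the study intervention may be replaced". Those who were treated and then left are not replaced. Section 6.4 uses all participants in each arm as the safety denominator.

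**The concern.** Two analysts who follow the text in good faith could report the primary result on different patients. One would keep all 150 under section 6.2.1; the other would drop culture-negative patients under section 4.3, and perhaps non-completers under section 4.4.6.1. With no primary set named, the choice could be made after the results are seen.

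The two kinds of removal differ in risk. A negative culture on the screening stool is a baseline fact. Completing the trial is not: section 4.11 lets investigators withdraw patients for disease progression, adverse events or non-compliance, all of which arise after randomisation and may depend on treatment.

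Two further problems follow. Section 4.3 acts on culture alone, while section 4.2.4 accepts culture or RT-PCR, so a culture-negative, RT-PCR-positive patient is eligible under one and removed under the other. And section 4.3 read literally takes dosed patients out of safety, against section 6.4.

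**Working it through.** **The rules side by side**

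| Place | Rule | Who is analysed |
|---|---|---|
| 4.3 | culture-negative patients out of the final analysis | culture-positive only |
| 4.4.6.1 | completers assigned to groups | completers only |
| 6.2.1, 6.3 | nothing subtracted from ITT | all randomised |
| 5.0 | ITT is 150 | all 150 |
| 6.4 | safety denominator | all participants per arm |

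Nothing assigns the first two rules to MITT or PP, so they cannot be squared with the others from the text alone.

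**Inputs for power (section 5.0)**

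- "Mean stool output was assumed at 280 ± 156 g/kg", so SD = 156.
- "Assuming 33% reduction (alternative hypothesis) vs no reduction (null hypothesis"), so delta = 0.33 × 280 = 92.4 g/kg and the standardised effect is 92.4 / 156 = 0.592.
- Two-tailed t-test, alpha 5%, target power 0.80, arms of equal size n.

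**Formula.** Power from the noncentral t distribution with 2n − 2 degrees of freedom and noncentrality delta / (SD × √(2/n)).

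**The plan's own figures**

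- n = 75: noncentrality 92.4 / (156 × √(2/75)) = 3.63, power 0.950 (stated 0.94).
- n = 50: noncentrality 2.96, power 0.835 (stated 0.82).

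Both agree to within two percentage points. The 0.94 therefore describes 75 analysed per arm, all with the full 33% effect.

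**With unconfirmed patients.** Let f be the share not confirmed. The documents give no value; 10% to 25% is an assumption, taken as equal in both arms with no other losses.

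- Removed: n = 75 × (1 − f), delta = 92.4.
- Kept, no drug effect in them: n = 75, delta = 92.4 × (1 − f).
- Kept, half the effect in them: n = 75, delta = 92.4 × (1 − f/2).

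The two kept rows also assume the same placebo mean and SD in unconfirmed patients.

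| f | Removed: n per arm | Removed: power | Kept, no effect: delta | Power | Kept, half effect: delta | Power |
|---|---|---|---|---|---|---|
| 10% | 67.5 | 0.927 | 83.2 | 0.900 | 87.8 | 0.928 |
| 20% | 60 | 0.896 | 73.9 | 0.822 | 83.2 | 0.900 |
| 25% | 56.25 | 0.876 | 69.3 | 0.771 | 80.9 | 0.884 |

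**How much removal the design can bear.** Power is 0.802 at 46 per arm and 0.794 at 45. Removal alone therefore keeps power at or above 0.80 until (75 − 46) / 75 = 39% are lost.

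**The case against.** The strongest reply is that section 5.0 already plans for losses. It treats 50 per arm as sufficient and offers 75 as protection against drop-out, cross-over, withdrawal and missing data. This stands. A reader might infer that the trial is underpowered or its power miscalculated; the documents support neither. The buffer does not name culture-negative patients, but it absorbs a moderate number. The only figure in the table below 0.80 needs both 25% unconfirmed and no effect at all in them. Section 4.4.4 places the drug's action at the intestinal mucosa, so no effect is a worst case.

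A reader might also infer that dropping culture-negative patients breaks randomisation. It need not. The confirmatory stool is collected at screening (section 4.5.1, Appendix I) and before antibiotics (section 4.10.3), in a double-blind trial. A population confirmed on that sample is legitimate once it is defined.

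The completer phrase in section 4.4.6.1 may be only loose wording about releasing the randomisation tables. Section 6.2.2 plans multiple imputation in ITT, section 6.2.1 places non-adherent and lost patients in groups, and section 7.1 retains data after withdrawal. So the documents do not show that a completer-only analysis is intended. They do contain a sentence that prescribes one, and it should not remain.

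Nor is replacement in section 4.11 a contradiction in itself: it does not say that replaced patients leave ITT. Finally, late knowledge of the result is shown for culture only. No RT-PCR turnaround is given, and RT-PCR is absent from the procedures in section 4.5 and Appendix I.

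**Conclusion.** The contradiction is in the current text and rests on no outside figure. Section 4.3 and section 4.4.6.1 each conflict with the no-subtraction rule, and the undefined MITT and PP and the missing primary set leave the conflict unresolved. The culture exclusion need not bias the comparison if it uses the pre-dose stool and is decided blind; restriction to completers can bias it.

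The power calculation is sound for what it describes. What is missing is a label for its population and an allowance for unconfirmed patients. Under the assumed 10% to 25%, power is 0.93 to 0.88 with removal; with all patients kept it is 0.90 to 0.77 (no effect in the unconfirmed) or 0.93 to 0.88 (half the effect). The point must be fixed because the analysis population has to be settled before unblinding, not because the trial is too small.

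**What to change.** 1. In section 4.4.6.1, assign all randomised participants to groups, not only completers.
2. In section 4.3, limit the removal of culture-negative patients to the MITT and PP sets.
3. Define ITT as all randomised patients, including any later replaced. Define MITT as all randomised and dosed patients with *V. cholerae* confirmed on the screening (pre-dose) stool, decided blind to arm. Define PP as MITT without major protocol deviations. Name one set as primary before unblinding and report the others as sensitivity analyses.
4. Keep all dosed patients in the safety set, as section 6.4 implies.
5. Go on recording stool output to 72 hours or recovery in patients whose study treatment is stopped, so that ITT has endpoint data.
6. In section 5.0, give the PP stopping clause a number or delete it, and say whether replacements count towards the 150.
7. Restate power for the named primary set at a stated, assumed confirmation rate.
8. Sections 4.2.4, 4.2.5 and 4.3 must be reconciled on which test (culture alone, or culture or RT-PCR) decides eligibility and stopping of treatment. No clinical rule is proposed here.

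The cost is mostly wording, and the stated power becomes slightly less favourable. Item 5 adds some data recording, but section 4.3 already keeps patients in hospital for the three days. If replaced patients stay in ITT and replacements do not count towards 150, somewhat more than 150 will be randomised. If the reconciled rule relies on RT-PCR, that test must be added to the schedule.
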